2.12. Simvastatin

- Treat with statins for 1-2 weeks, up to 4-6 weeks, and maintain during long-term treatment.
- Simvastatin largely excreted in the feces. Approximately 10-15% of the drug excreted by the kidney
- Dosage is 5-80 mg/day, in the evening.
- No dosage adjustment is needed in the elderly
- **Contraindications of Simvastatin:**
 - + Active liver disease or unexplained persistent elevations of serum transaminases

- + Pregnancy and lactation
- + Concomitant administration of potent CYP3A4 inhibitors (e.g. itraconazole, ketoconazole, posaconazole, HIV protease inhibitors (e.g. nelfinavir), erythromycin, clarithromycin, telithromycin, and nefazodone)
- + Concomitant administration of gemfibrozil, ciclosporin, or danazol.
- **Unexpected effects of Simvastatin and how to manage unexpected effects**
 - + **Myopathy:** The risk of myopathy is related to dose. In a clinical trial of 41,413 patients treated with simvastatin, 24,747 patients (about 60%) with an average follow-up of at least 4 years, the incidence of myopathy was approximately 0.03%, 0.08% and 0, 61% at doses of 20, 40 and 80 mg/day, respectively.
 - If the patients have muscle aches, weakness or cramps, do CK test. If CK increases (> 5 times) discontinue treatment, re-assess levels within 5 to 7 days.
 - If the muscular symptoms are severe and cause daily discomfort, even if the CK levels are < 5 times normal, consider stopping treatment.
 - + **Elevated liver enzymes:** Continuous elevations (up to > 3 times) liver enzymes have occurred in some patients receiving simvastatin.
 - When simvastatin is discontinued, the level of transaminase usually decreases gradually down to the pre-treatment level.

+ **Diabetes Mellitus**

Some evidence suggests that statins as a class raise blood glucose and in some patients, at high risk of future diabetes, may produce a level of hyperglycemia where formal diabetes care is appropriate. This risk, however, is outweighed by the reduction in vascular risk with statins and therefore should not be a reason for stopping statin treatment.

+ Other side effects: Dizziness, fainting, fast or irregular heartbeat,...

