2.13. Ezetimibe

- Ezetimibe inhibits the intestinal absorption of cholesterol, which reduces cholesterol from the small intestine into the liver.
- Dose may be 10-40mg / day
- Ezetimibe is metabolized mainly in the small intestine and liver, excreted in the bile.
- No dosage adjustment in elderly patients, patients with CKD
- Hepatic impairment: EZE is not known in patients with moderate or severe liver failure, should not be used.
- Patients with chronic kidney disease / renal disease
 - + Monotherapy: No need to adjust the dose of Ezetimibe.
 - + Combination with Simvastatin:
 - No dose adjustment of Ezetimibe or simvastatin in patients with GFR ≥ 60 mL/min / 1.73m².
 - In patients with GFR < 60 mL / min / 1.73m²), the dose of Ezetimibe is 10 mg and simvastatin is 20 mg once daily, taken in the evening. Patients should be monitored if higher doses of simvastatin are used.

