4. METHODOLOGY

4.1. Study design: A prospectively study with clinical trials, 12 months follow up.

4.2. Subject: 30 patients with hypercholesterolemia (LDL-C), stage 3-4 Chronic Kidney Disease, not receiving dialysis and 30 control participants (sex, age-matched)

4.2.1. Inclusion Criteria:

30 patients with following criteria

- CKD in the 3,4 stage (e-GFR: 15-60 ml/min/1.73 m²)
- Presence of proteinuric CKD defined as creatinine clearance >20 ml/min/1.73 m² combined with urinary protein excretion rate >0.3 g/24 h
- LDL cholesterol concentration > 100 mg/dl (2,59 mmol/l)
- Age:
 - + ≥ 50 years old but not treated with chronic dialysis or kidney transplantation
 - + In adults aged 18-49 years with CKD but not treated with chronic dialysis or kidney transplantation, we suggest statin treatment in people with one or more of the following:
 - known coronary disease (myocardial infarction or coronary revascularization)
 - diabetes mellitus
 - prior ischemic stroke
 - estimated 10-year incidence of coronary death or non-fatal myocardial infarction > 10%

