4.6. Procedure

- Potentially eligible patients attended a screening visit in an internal examination room or internal department of Hue University Hospital for medical history and other eligibility criteria checked.

- Fasting blood samples will be taken for local laboratory assays lipid profile, proteinuria, urea and creatinine, creatine kinase, SGOT, SGPT, total blood count, total haemostasis test

- If the patient satisfies the including criteria, written informed consent obtained 30 enrolled patients will be randomized into 3 groups and will receive one of 3 lipid-lowering therapies at the baseline and continue for 12 months

Group 1: (10 participants) receive 40 mg/day simvastatin (patient No 1, 4, 7...)

Group 2: (10 participants) receive ezetimibe/simvastatin 10/20 mg/day: (patient No 2, 5, 8...)

Group 3: (10 participants) receive ezetimibe/simvastatin 10/40 mg/day: 10/40: (patient No 3, 6, 9...)

- Patients will follow the treatment for 12 months and will be seen in the study clinics for routine follow-up checks and blood test at 4, 8, and 12 months.

- At each follow-up time, study treatment will be continued, unexplained muscle pain and non-study treatment recorded.

Patients are asked for an unscheduled visit if they want to have any additional review.

- If patients are unable or unwilling to attend the follow-up checks, ask them if they have any serious adverse events.

- The blood samples will be sent to Biochemical Department of Sassari University for oxidative stress indices and Tryptophan degradation indices every 4 months.

5. Biochemical analysis

- Serum Creatinine, GFR, urine protein, lipid profile, SGOT, SGPT, CK (Total Cholesterol, LDL-C, HDL-C, TG): Will be done in Hue University hospital/Hue Central Hospital.

+ Total Cholesterol, LDL-C, HDL-C, and TG were measured by enzymatic methods using commercial kits (Boehringer-Mannheim, Mannheim, Germany): Patients must fast for at least 12 hours before the test

+ Serum CK levels were measured by using a fully automated biochemical analyzer (Abbot).

+ Proteinuria

+ Serum urea, creatinine

+ Total cells blood count

+ Total hemostasis test

[Time Frame: at baseline and 4, 8, 12 months of treatment]

- Serum concentrations of Oxidative stress indices (MDA, All/UA, Taurine), Trp degradation indices (Kyn, Trp, Kyn/Trp ratio): Will be done in Sassari University hospital.

MDA, All/UA ratio, taurine, Kyn, Trp were determined by capillary electrophoresis UV detection.

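### Section 4.6 continues study drug at every visit and ties no action to the scheduled SGOT/SGPT results, although section 2.12 lists a persistent unexplained rise as a simvastatin contraindication

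*Protocol*

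**What the plan says.** Protocol section 4.5 gives simvastatin to every arm for 12 months: 40 mg alone, 20 mg with ezetimibe, or 40 mg with ezetimibe. Section 4.6 sets clinic visits with blood tests at months 4, 8 and 12, and section 5 includes SGOT, SGPT and CK among the assays at baseline and at those months.

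For the visits themselves, section 4.6 says: "At each follow-up time, study treatment will be continued, unexplained muscle pain and non-study treatment recorded". It does not mention liver results.

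Section 2.12, in the literature review, has a heading that promises guidance on managing simvastatin's side effects. On muscle it gives a sequence: "If the patients have muscle aches, weakness or cramps, do CK test", then "If CK increases (> 5 times) discontinue treatment, re-assess levels within 5 to 7 days". It adds that stopping should be considered for severe symptoms at lower CK. On liver enzymes it has two sentences: "Continuous elevations (up to > 3 times) liver enzymes have occurred in some patients receiving simvastatin" and "When simvastatin is discontinued, the level of transaminase usually decreases gradually down to the pre-treatment level". Among the contraindications it lists "Active liver disease or unexplained persistent elevations of serum transaminases".

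The exclusion criteria in section 4.2.2 name no liver condition. The SAP contains no safety or stopping rule.

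**The concern.** The trial collects liver enzymes on treatment but does not say what anyone should do with them. The protocol regards liver effects as a real question: the background associates high statin doses with hepatotoxicity, research question 4 asks about the hepatic enzyme profile, and objective 2 compares side effects between regimens.

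The patient's safety is at stake. Someone can develop on study a condition that the protocol itself calls a contraindication, while the written visit instruction is to carry on. Section 2.12 says that levels usually come back down once the drug is stopped, so continuing exposes the patient to a risk that stopping would probably remove. If clinicians do stop the drug, the threshold and timing are left to each of them.

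**Working it through.** The plan states no figure to reproduce. The check is a comparison of texts, followed by two small calculations.

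**Step 1. What each place says about muscle and liver.**

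| Element | Muscle / CK | Liver / SGOT, SGPT |
|---|---|---|
| Measured at months 4, 8, 12 (section 5) | yes | yes |
| Recorded at visits under section 4.6 | muscle pain | nothing named |
| Trigger for a test outside the schedule (section 2.12) | symptoms | none |
| Numerical limit for action (section 2.12) | CK > 5 times | none |
| Instruction to stop (section 2.12) | yes | none |
| Re-assessment interval (section 2.12) | 5 to 7 days | none |
| Listed as a contraindication (section 2.12) | no | yes, if persistent and unexplained |
| Carried into section 4.2.2 or 4.6 | no | no |

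The figure of 3 times in the liver entry describes what has been observed in patients. It is not attached to an instruction and cannot serve as a threshold as it stands. The CK rule is triggered by symptoms and is not referred to in section 4.6, so the methods section contains no explicit stopping rule of either kind. The difference is that a CK rule exists elsewhere in the protocol and a liver rule does not.

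**Step 2. How long a patient could stay on drug.** Inputs: 12 months of treatment (section 4.5) and visits at months 4, 8 and 12 (section 4.6). A rise first seen at month 4 can be called persistent at the next scheduled test, month 8. If nobody acts before the end:

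- months left after month 8 = 12 − 8 = 4
- share of the treatment period = 4/12 = 33%

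**Step 3. How many patients.** Neither document gives a rate of confirmed elevation, so the number cannot be derived. As an assumption only, let p be the risk per patient over 12 months. With 30 treated patients (section 4.2), the expected number is 30p and the chance of at least one case is 1 − (1 − p)^30.

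| Assumed p | Expected cases | Chance of at least one |
|---|---|---|
| 0.5% | 30 × 0.005 = 0.15 | 1 − 0.995^30 = 14% |
| 1% | 30 × 0.01 = 0.3 | 1 − 0.99^30 = 26% |
| 3% | 30 × 0.03 = 0.9 | 1 − 0.97^30 = 60% |

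The expected count is below one patient throughout this range. The case for a written rule does not depend on which row is true.

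**The case against.** **The section 4.6 sentence is only a default.** It reads as a list of routine visit activities. It does not mention CK either, yet section 2.12 plainly has patients stopping for CK, so it cannot be an absolute order to continue. This stands. A reader might infer that sections 4.6 and 2.12 contradict each other. The documents do not support that, because a default can coexist with exceptions. What is missing is a written exception for liver results.

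**Section 2.12 already points to stopping.** Its liver entry sits under a heading about management, speaks of what happens after discontinuation, and is accompanied by the contraindication. A careful clinician could put these together and stop the drug. That is fair, but there is no limit, confirmation step, timing or instruction, and section 4.6 makes no reference to section 2.12. The heading also cuts the other way, since it promises management and the liver entry supplies none.

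**Group 3.** Section 2.13 gives simvastatin 20 mg with ezetimibe when GFR is below 60, and adds: "Patients should be monitored if higher doses of simvastatin are used". Entry requires an eGFR of 15 to 60 and Group 3 receives 40 mg with ezetimibe, so a reader might infer that the plan fails this arm in particular. It does not. Section 2.13 asks for monitoring, and the plan monitors. The missing action applies equally to all three arms.

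**Bias between arms.** A reader might also infer that discretionary stopping distorts the comparison of side effects. Nothing in the documents shows that stopping would differ by arm, and with less than one expected case under the assumptions above, that argument is speculative.

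**Longer exposure.** One could count 8 of 12 months from a rise first seen at month 4. That rise is not yet confirmed or persistent, so 8 months overstates the exposure of a patient with an established problem.

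**Text not seen.** The protocol's section numbers jump from 5 to 7, so a rule elsewhere cannot be wholly ruled out. Section 4.6 refers to none.

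**Conclusion.** The point holds as a gap in patient safety. Both documents schedule or analyse laboratory results, but neither links an SGOT or SGPT value to a repeat test, an interruption or a stop, and the one instruction that covers the visits is to continue. Read as written, a patient with a persistent rise could take study drug to month 12, which is 4 further months after persistence is visible at month 8. That figure assumes that nobody acts between or at the scheduled visits. The number of patients affected is unknown and may be zero.

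This does not show a contradiction within the protocol, a bias between arms or a fault peculiar to Group 3. The change is worth making because it protects patients, uses tests already planned and costs little. Confidence is medium, since clinicians may well stop the drug without a written rule.

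**What to change.** Amend section 4.6 so that continuing at months 4 and 8 is conditional, in the same terms for all three arms:

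- If SGOT or SGPT exceeds a limit set by the investigators (for example 3 times the upper limit of normal), repeat the test promptly.
- Stop study drug if the rise is confirmed and no cause other than study drug accounts for it. This wording matters: a rise attributed to simvastatin is no longer unexplained, and it should still lead to stopping.
- Cross-refer to the CK rule in section 2.12, keeping its symptom trigger, its limit and its re-assessment interval.
- Record the date and reason for each stop.
- Keep stopped patients in the scheduled visits and sampling, and analyse them in their assigned group. One sentence in the SAP should say so.

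The cost is a short amendment, occasional repeat tests and a few discontinuations. Each discontinuation is 1 of 10 patients, or 10% of an arm, and weakens the on-treatment contrast in that arm. Continued sampling keeps that patient's series complete for the repeated-measures ANOVA in the SAP.

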(1) Do different lipid-lowering drugs (simvastatin monotherapy and ezetimibe/simvastatin combination therapy) have a different impact on the lipid profile, oxidative stress indices, Tryptophan degradation?

(2) Does statin monotherapy or co-administration of ezetimibe ameliorate the renal dysfunction in CKD patients?

(3) How do lipid-lowering therapy effect on lipidemia disorders in patients with CKD by mechanism involved in oxidative stress and tryptophan?

(4) Are the unexpected effects on muscle problem and hepatic enzyme profile of long-term statin monotherapy and statin/ezetimibe combination therapy a big concern?

II. REVIEW OF RESEARCH LITERATURE

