2.14. New York Heart Association class III (McMurray et al., 2012)

Classification of heart failure symptoms

Class I	People whose physical activity is not limited. Ordinary physical activity does not cause undue fatigue, heart palpitations, trouble breathing, or chest pain.
Class II	People who have some limitation on physical activity. They are comfortable at rest, but ordinary physical activity causes fatigue, heart palpitations, trouble breathing, or chest pain.
Class III	People who have a marked limitation on physical activity. They are comfortable at rest, but less-than-ordinary physical activity causes fatigue, heart palpitations, trouble breathing, or chest pain.
Class IV	People who are unable to carry on any physical activity without discomfort. Symptoms may be present even at rest. If any physical activity is done, discomfort increases.

2.15. 2017 Taiwan lipid guidelines for high-risk patients

LDL-C increased CV risk in patients with CKD. In adults with glomerular filtration rate (GFR) < 60 mL/min/1.73m² without chronic dialysis (CKD stage 3-5), statin therapy should be initiated if LDL-C ≥ 100 mg/dL. Ezetimibe can be added to a statin to consolidate the CV protection in CKD patients (Li et al., 2017)

3. Objective of the research

The target of this study is to focus on mechanisms underlying dyslipidemia in CKD and clinical trial evidence for lipid lowering therapy in patients with CKD via parameters of lipid, oxidative stress, tryptophan degradation as well as renal function, in comparison to statin/ezetimibe therapies in CKD patients with dyslipidemia.

- 1) To verify the effect of lipid lowering therapies on lipid profile and inflammatory status in Vietnamese CKD population. [Time Frame: at the baseline and at 4th month, and one-year following].
- 2) To compare the effect of lipid-lowering regimes (simvastatin mono-therapy and EZE/simvastatin 10/20, EZE /simvastatin 10/40 combination therapy) on lipid profile, oxidative stress indices, Tryptophan degradation, renal parameter, and side effect in Vietnamese CKD patient. [Time Frame: after the 4th month, 8th month and one-year following].

We hope with scientific evidence, doctors will well understand the mechanism, effect, and safety of potential and existing therapies. Therefore, the prescription rate of lipid-lowering drugs and control rate of hyperlipidemia could be increased in CKD

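### Follow-up visits must record only unexplained muscle pain, a narrower and more judgement-dependent record than the protocol's own background text implies, and no muscle outcome is defined or analysed

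*Protocol*

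**What the plan says.** **What visits record.** Protocol section 4.6 has patients seen at 4, 8 and 12 months, with "unexplained muscle pain and non-study treatment recorded". Neither document says anything else about which muscle symptoms to record. Section 4.6 also allows unscheduled visits at the patient's wish, and has patients who cannot or will not attend asked about serious adverse events.

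**What the background text names.** Section 2.12, on managing the unwanted effects of simvastatin, reads: "If the patients have muscle aches, weakness or cramps, do CK test". It attaches no condition on cause. It goes on to a case that begins "If the muscular symptoms are severe and cause daily discomfort", and it allows for that case with CK below 5 times normal.

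**What the trial asks.** Research question 4 in section I is: "Are the unexpected effects on muscle problem and hepatic enzyme profile of long-term statin monotherapy and statin/ezetimibe combination therapy a big concern"? Objective 2 in section 3 compares the regimens on, among other things, "renal parameter, and side effect in Vietnamese CKD patient". Neither the muscle problem nor the side effect is defined.

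**Laboratory measurement.** Section 5 lists CK for all patients: "Serum CK levels were measured by using a fully automated biochemical analyzer (Abbot", with "Time Frame: at baseline and 4, 8, 12 months of treatment".

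**Analysis.** The SAP covers laboratory values and correlations. It gives no count, rate or comparison of any muscle symptom.

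**The concern.** Side effects are one of the things objective 2 compares between the three regimens, and the muscle is one of two systems named in research question 4. Any answer about symptoms has to come from what visits write down. The 4.6 wording narrows that record in two ways. It names pain only, so weakness or cramps need not be entered. It also names only pain that is unexplained, so pain put down to exercise or arthritis falls outside it.

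The second restriction matters more for a comparison. Someone must decide at the visit whether the pain has another cause, and the protocol gives no criteria and names no assessor. Neither document describes masking. Section 4.6 ties regimen to patient number in a fixed sequence of three, so the number alone reveals the arm. Section 2.12 tells the reader that myopathy risk rises with dose. An assessor who knows the regimen could therefore judge similar pain differently in different arms.

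**Working it through.** The documents give no power, rate or event figure for muscle symptoms, so there is no plan figure to reproduce. The check is a comparison of texts, followed by an illustration on assumed rates.

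**1. The wordings side by side**

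| Place | Symptoms named | Condition on cause | Role |
|---|---|---|---|
| Protocol 4.6 | pain | must be unexplained | what visits record |
| Protocol 2.12 | aches, weakness, cramps | none | background; prompts a CK test |
| Research question 4 | muscle problem | not stated | question |
| Objective 2 | side effect | not stated | comparison of regimens |
| SAP | none | – | no symptom analysis |

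The 4.6 line is the narrowest, and it is the only one that governs recording.

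**2. Whether other routes fill the gap**

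- CK at baseline, 4, 8 and 12 months detects enzyme rises in any patient, whatever the symptom. It does not record symptoms that occur without a rise, and 2.12 itself allows for severe symptoms with CK below its 5-fold threshold.
- An unscheduled visit depends on the patient asking for one, and no recording rule is attached to it.
- The question for patients who miss visits covers serious events only.

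These routes reduce the gap but do not close it.

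**3. What the protocol's own rates imply**

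Section 2.12 cites myopathy rates of 0.03% at 20 mg and 0.08% at 40 mg of simvastatin. With 10 patients per arm, one arm on 20 mg and two on 40 mg:

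- Expected cases = 10 × 0.0003 + 20 × 0.0008 = 0.003 + 0.016 = 0.019.
- Chance of at least one = 1 − (1 − 0.0003)^10 × (1 − 0.0008)^20 = 1.9%.

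This ignores any added effect of CKD or ezetimibe. On these rates, nearly all clinical muscle data would be milder symptoms, which are the ones the 4.6 wording narrows.

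**4. Illustration on assumed rates**

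Let r be the true share of patients with any ache, weakness or cramp, and s the share of those who meet the 4.6 wording. The documents give neither. Assume r of 5% to 20% and s of 50% to 80%. The recorded rate is r × s, and the chance that an arm of 10 shows no case is (1 − rate)^10.

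| r | Affected of 30 | Recorded of 30 (s = 50% to 80%) | No case in 10, full record | No case in 10, 4.6 record (s = 80% to 50%) |
|---|---|---|---|---|
| 5% | 1.5 | 0.75 to 1.2 | 0.95^10 = 60% | 0.96^10 = 66% to 0.975^10 = 78% |
| 10% | 3 | 1.5 to 2.4 | 0.90^10 = 35% | 0.92^10 = 43% to 0.95^10 = 60% |
| 20% | 6 | 3 to 4.8 | 0.80^10 = 11% | 0.84^10 = 17% to 0.90^10 = 35% |

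For differential judgement, suppose two arms share a true 20% and the pain is called unexplained in 90% of cases in one arm and 60% in the other. The records show 0.20 × 0.90 = 18% against 0.20 × 0.60 = 12%, with no real difference. In arms of 10 that is 1.8 against 1.2 expected patients.

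**The case against.** The strongest reply has four parts.

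**Section 2.12 is background.** It sits in the literature review and gives a trigger for a CK test. A reader might infer that the protocol holds two conflicting definitions of the muscle outcome. The documents do not support that, because they contain no definition of it at all. This part stands.

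**Nothing is excluded.** A reader might also infer that weakness, cramps and explained pain are never counted. That goes too far. Section 4.6 does not forbid recording them, CK is measured in everyone, a CK test prompted as in 2.12 would leave a trace, and patients may ask for extra visits. This stands as a limit on the claim. It remains true that no one is required to record these symptoms.

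**No planned estimate is biased.** The SAP plans no symptom analysis, so the 4.6 wording distorts no specified result. This also stands, but it shows a second gap: a stated comparative objective has neither a defined symptom outcome nor an analysis.

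**Restricting to unexplained pain is a defensible trade.** Many patients will be 50 or older and have aches from other causes, so a narrower record is more specific. That is a fair reason to keep the unexplained subset. It does not justify discarding the rest at the point of recording, because a subset can be formed later from a full record but not the other way round.

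The illustration also has limits. Every rate in it is assumed, and 1.8 against 1.2 patients could not be told apart from chance. That assessors would in fact judge by arm is a possibility, not something the documents show.

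**Conclusion.** The point holds as a gap in recording and definition. The only rule on which muscle symptoms to record is narrower than the list in the protocol's own background text and depends on an unmasked causal judgement without criteria. The outcome it should serve is undefined and unanalysed. The symptom record may therefore be incomplete in every arm and is open to differential recording.

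The size cannot be derived from the documents. Under the assumed ranges, the chance that an arm of 10 shows no case rises from 11% to between 17% and 35% at a true rate of 20%, and from 35% to between 43% and 60% at 10%. These figures show sensitivity to the wording and are not estimates for this trial. Even with a full record, 10 patients per arm allow only description: with no case in 10, the exact two-sided 95% upper limit is 1 − 0.025^(1/10) = 31%. The correction is worth making because a stated objective depends on it and it costs little.

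**What to change.** **Protocol 4.6.** Replace the muscle-pain item with three yes/no items (aches, weakness, cramps), asked of every patient at each visit and entered whatever the suspected cause. Put the suspected cause in a separate field. This reconciles the recording rule with the symptoms listed in 2.12. The clinical management rules in 2.12 are not changed.

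**Protocol, research question 4 and objective 2.** State that the muscle symptom outcome is any of the three items at any follow-up visit.

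**SAP.** Report by arm the number of patients with any such symptom, with the unexplained subset as secondary. Keep this descriptive, given 10 patients per arm.

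**Cost.** One procedure line, a few form fields and one table. The background rate of symptoms not due to the drugs will be higher. Self-report also remains open to bias while patients and staff may know the regimen: separating the symptom from its cause takes the causal judgement out of the main count but does not replace masking.

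### Section 4.6 states a serious adverse event question for non-attenders only, muscle-pain recording for clinic follow-up times only, and no baseline muscle-symptom question, so followed literally the counts depend on attendance

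*Protocol*

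**What the plan says.** Protocol Section 4.6 says that patients "will be seen in the study clinics for routine follow-up checks and blood test at 4, 8, and 12 months". Two instructions on events follow.

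- For the follow-up times: "At each follow-up time, study treatment will be continued, unexplained muscle pain and non-study treatment recorded".
- For patients who do not come: "If patients are unable or unwilling to attend the follow-up checks, ask them if they have any serious adverse events".

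The second is the only serious adverse event instruction in either document. Patients may also ask for an unscheduled visit, but no event question is attached to it. Screening in the same section covers medical history, eligibility and blood tests, and muscle symptoms are not named. Section 5 schedules CK, SGOT and SGPT at baseline and at months 4, 8 and 12.

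Side effects are among the trial's questions. Objective 2 (Section 3) compares the three regimens on "lipid profile, oxidative stress indices, Tryptophan degradation, renal parameter, and side effect in Vietnamese CKD patient". Research question 4 (Section I) asks: "Are the unexpected effects on muscle problem and hepatic enzyme profile of long-term statin monotherapy and statin/ezetimibe combination therapy a big concern". The SAP covers laboratory values and correlations and plans no analysis of symptoms or serious adverse events.

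**The concern.** A comparison of side effects between arms needs the same question put to every patient at the same times. Section 4.6 instead states one question for those who come and a different one for those who do not. Taken at its word, a patient admitted to hospital between two attended visits is not asked about the admission. A patient who stays away because of muscle pain is not asked about the pain.

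Two consequences follow. First, the recorded counts depend on attendance as well as on the drugs. If attendance differs by arm, for instance because tolerability differs, the counts would differ even where the true risks are equal. Second, with no muscle-symptom record before the first dose, pain reported at month 4 may have been there already. This second problem does not depend on attendance.

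The item recorded is also limited to pain judged unexplained. That is a site judgement, and neither document describes blinding.

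**Working it through.** The plan gives no event rate, attendance rate or dropout figure, so there is nothing of its own to reproduce. The first step sets the instructions side by side.

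| Item | Baseline | Attended visit (months 4, 8, 12) | Missed visit |
|---|---|---|---|
| Muscle symptoms | not named; general medical history taken | recorded if judged unexplained | not stated |
| Serious adverse events | before treatment | not stated | asked |
| CK, SGOT, SGPT | measured | measured | no sample |

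The two symptom and event rows have no follow-up column in common. The laboratory row is uniform apart from missed samples.

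The second step is an illustration on the literal text. The one input from the documents is *n* = 10 per arm (Section 4.6: "Group 1: (10 participants) receive 40 mg/day simvastatin", and the same number in the other two arms). Everything else is assumed: attendance *a*, true serious-event risk *s* and true muscle-pain risk *m*, equal in all arms, with attendance unrelated to events and one contact at which each event would come to light.

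- Expected serious events solicited per arm = *n* × *s* × (1 − *a*)
- Expected muscle-pain cases recorded per arm = *n* × *m* × *a*

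| Attendance | Serious events, *s* = 10% (true 1) | Serious events, *s* = 20% (true 2) | Muscle pain, *m* = 20% (true 2) |
|---|---|---|---|
| 100% | 0 | 0 | 2.0 |
| 90% | 0.1 | 0.2 | 1.8 |
| 70% | 0.3 | 0.6 | 1.4 |
| 50% | 0.5 | 1.0 | 1.0 |

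The two counts move in opposite directions as attendance falls. With true risks of 20% for both event types, an arm at full attendance and an arm at 70% would show 0 against 0.6 serious events and 2.0 against 1.4 muscle-pain cases, where the truth is 2 of each in both arms. At full attendance the solicited serious-event count is zero whatever the true risk; that result needs no assumed rate.

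The denominator matters. If attendance is unrelated to pain, dividing by those asked restores the muscle-pain rate: 1.4 / 7 = 20%. The same works in principle for serious events, 0.6 / 3 = 20%, but it rests on three patients, and at full attendance nobody has been asked.

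The third step lets pain affect attendance. If patients with pain attend with probability *p* and others with probability *q*, the rate among attenders is *m p* / (*m p* + (1 − *m*) *q*).

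- *m* = 0.20, *p* = 0.60, *q* = 0.90: 0.12 / (0.12 + 0.72) = 14.3%.
- *m* = 0.20, *p* = 0.50, *q* = 0.95: 0.10 / (0.10 + 0.76) = 11.6%.

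Here the right denominator does not rescue the estimate; only asking the non-attenders does.

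The fourth step is the missing baseline. With pre-existing pain *b* and new onset *i* among the rest, on-treatment pain is *b* + (1 − *b*) × *i*.

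- *b* = 10%, *i* = 10%: 0.10 + 0.90 × 0.10 = 19%.
- *b* = 20%, *i* = 10%: 0.20 + 0.80 × 0.10 = 28%.

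If every patient is reached and asked the same questions, the expected counts become *n* × *s* and *n* × *m* at any attendance: 1 to 2 serious events per arm for *s* of 10% to 20%, and 1 to 3 muscle-pain cases for *m* of 10% to 30%.

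**The case against.** The strongest reply is that the restriction is read from silence. Section 4.6 does not forbid asking attenders about serious events. The sentence on non-attenders can be read as a fallback: those who come are seen and checked, and those who cannot come are at least asked about the worst outcomes. Likewise, the muscle-pain instruction refers to follow-up times, which could include a telephone contact. Medical history at screening might pick up earlier muscle complaints, the word unexplained leaves room to set aside pain with a known cause, CK is measured from baseline onward, and a troubled patient may ask for an unscheduled visit.

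Much of this stands. A reader might infer that the protocol bars the serious-event question for attenders, or that pre-existing pain could never be recognised; the documents support neither. They also do not support the inference that the whole side-effect comparison is compromised, because CK and the liver enzymes follow one schedule in all arms. A false difference between arms requires attendance to differ by arm, and nothing in the documents shows that it will.

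What remains is that the comparison would rest on practice that is not written down. The section describes follow-up as clinic visits, names only serious events for those who miss them, and attaches no event question to the patient-initiated visit. CK is not a symptom record and is also lost when a visit is missed. The symptom-triggered CK test in Section 2.12 starts from symptoms the patient already has, and it sits in the literature review as a management note.

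**Conclusion.** The concern holds in this limited form. Section 4.6 states no serious adverse event question for attenders, no muscle-pain question for non-attenders and no baseline muscle-symptom question. Followed literally, symptoms and serious events are under-ascertained in a way that depends on attendance. They would differ falsely between arms if attendance did, and new muscle symptoms could not be separated from old ones. It bears on Objective 2 for both event types and on research question 4 for muscle symptoms only.

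The size of the bias cannot be estimated from the documents. Attendance, risks and baseline prevalence in the working are all assumptions, and the counts assume that no attender's serious event is captured by another route. A reader might be tempted to attach a ratio to the false difference, for example six-fold if one arm misses 1 visit and another 6. The risk cancels from that ratio, so it merely repeats the assumed 6 to 1 split. At an assumed 5% risk per interval the absolute gap would be 6 × 0.05 − 1 × 0.05 = 0.25 expected events. The case for change rests on unequal ascertainment, which is cheap to correct now; events not asked about at the time may not be reliably recovered later.

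**What to change.** Add to Section 4.6 and keep its present text, including the recording of non-study treatment.

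- At baseline, before the first dose, record any current muscle pain, weakness or cramps.
- At months 4, 8 and 12, ask every patient the same two questions, in clinic or by telephone if the patient does not attend: any muscle pain, weakness or cramps since the last contact, and any serious adverse event since the last contact.
- Record the judgement that muscle pain is unexplained as a separate item, so that the symptom is kept whatever the judgement.
- In the SAP, add a table by arm of serious adverse events and of muscle symptoms that are new or worse than at baseline, with the number of patients asked as denominator.

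The cost is one added paragraph, one short form, one table and a few minutes per contact, with no extra clinic visits or tests. The reported counts will probably be higher than under the present text.
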